- **Duplicate pooled blood, urine, or saliva samples** will be included in each assay batch (~5-10% of samples) for QA and to assess inter- and intra-assay coefficient of variation. Baseline and follow-up samples from each participant will be assayed within each batch (paired), and paired samples will be randomly placed across batches. Laboratory personnel will be blinded with regard to subject and QA sample identity.
- VEGF and IL-6 will be assayed in serum samples at the Clinical and Epidemiologic Research Laboratory, at the Department of Laboratory Medicine, Boston Children's Hospital, Boston, MA, using Enzyme Linked Immunosorbent Assays from R&D Systems (R & D Systems, Minneapolis, MN). We have collaborated with this lab on a variety of studies: in our experience of working with them their assay performance as evaluated by CV and precision in our blind duplicate samples has out-performed other labs that we have worked with in the past, especially in difficult to measure analytes such as cytokines. The lab has extensive experience working with large cohort studies and randomized controlled trials including WHI.
- Cortisol will be assayed from saliva samples at the Salimetrics Lab and Technology Center (Salimetrics, LLC Carlsbad, CA) using the Salimetrics [Cortisol ELISA Kit](#) . Salivary cortisol correlates well with serum cortisol levels

(105). Salimetrics specializes in salivary biomarker assays, and in the development of saliva collection protocols and vials. Salimetrics has developed a Cortisol Enzyme Immunoassay Kit, a competitive immunoassay specifically designed and validated for the quantitative measurement of salivary cortisol. An independent research study in 2012 measured cortisol levels in 195 saliva specimens using a reference method (mass spectrometry) compared with the most popular immunoassays. The study reported that the Salimetrics assay was the most accurate and reliable of available commercial assays (106). Norepinephrine will be assayed from urine samples at the Department of Laboratory Medicine, Children's Hospital Boston, using the validated Noradrenaline Research Enzyme Linked Immunosorbent Assays from LDN (Labor Diagnostika Nord GmbH & Co.KG, Germany).

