7.4 Duration of Therapy

After baseline assessments (done at FHCRC Prevention clinic or home-based, see section 8.1) and randomization, participants randomized to the exercise arm will receive a one-on-one session with the exercise physiologist for one hour either at the FHCRC Prevention Center or through Telehealth. The exercise intervention will last for 24 weeks. During the intervention, they will not have any clinic visits. They will receive weekly telephone calls for support. All assessments during the intervention (actigraphy, surveys) will be completed at home. At the end of the study, all participants (exercise intervention arm and wait-list control arm) will complete end-of-study assessments either at clinic, or home-based (see section 8.1). After 24 weeks, participants in the wait-list control arm will be offered the home-based exercise intervention, which would also last for 24 weeks. Participants receiving the delayed intervention will be offered the single one-on-one session with the exercise physiologist and receive weekly telephone calls for support, but will not have any additional clinic visits or any assessments during or after the delayed intervention. Participants who were enrolled but ultimately became ineligible by falling significantly outside of the eligibility window (within 6 months of completing chemotherapy) before the baseline visit could occur due to COVID-19 related delays in visit scheduling. They may receive the exercise program without any data collection activities if they have a strong interest. We anticipate this to be a rare event going forward since baseline visits will now be allowed remotely, but rarely occurred previously due to prior COVID-19 related delays in Prevention Center scheduling and patient concern about visit timing.

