8.0 SUBJECT EVALUATION

8.1 On-Study Clinical Evaluations

Clinical evaluations take place according to the Study Calendar (Appendix C). Baseline assessments will occur prior to randomization, and whenever possible no later than 1 month after informed consent is signed. End-of-study assessments will occur at 24 weeks. The window between this end-of-study visit should be as close to 24 weeks as possible. The study team will make every effort to schedule this visit between 22 weeks and 26 weeks. Baseline and end-of-study visits originally were conducted at the FHCRC Prevention Center. Due to the COVID-19 pandemic and desire to expand clinical trial access to those who are unable or unwilling to travel to Seattle, participants will now be given a choice to have study assessments performed in clinic at the Prevention Center, or near to home/ at home. Participants desiring to avoid clinic visit will have blood collection performed at a local laboratory and continue to collect saliva at home. Collected blood and saliva will be shipped overnight to the FHCRC Prevention Center for specimen processing and storage. Urine collection, vitals, and anthropometrics will be omitted.

Additional assessments (such as surveys or actigraphy) will be performed at intervals throughout the study, but these assessments will be done at home. These assessments will be scheduled according to the Study Calendar, at the specified time point \pm 2 weeks, or as close as possible to that time window.

The following tests and procedures are completed, although not all tests may be done at each assessment point; see the detailed study timeline in Appendix C.

- **Anthropometrics and vitals:** Blood pressure, resting pulse, weight (in light clothing but without shoes), height (without shoes), waist (smallest diameter) and hip (largest diameter) circumferences. BMI (kg/m^2) will be calculated as weight (kg) divided by height squared (m^2). Participants who opt against a clinic visit will weigh themselves at home and report to us. If available, a recorded height will be abstracted from medical records, and if not available, self-report from the participant will be used. Vitals and anthropometrics will be omitted.

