- **Salivary Cortisol:** Participants will collect saliva samples at bedtime for 3 consecutive days at home. They will be asked to refrain from food, drink, caffeine, and exercise for 30 minutes before sample collections, and will be instructed to refrain from brushing or flossing teeth prior to sample collection. They will collect the saliva samples using the "passive drool" method. Sterile cryovials are fitted with a mouthpiece (Saliva Collection Aid) provided in the collection kit (Salimetrics, Carlsbad, CA). Participants are instructed to allow saliva to pool in the mouth. With head tilted forward, participants should drool through the Saliva Collection Aid to collect saliva in the 2 mL cryovial. The procedure is repeated until sufficient sample is collected. They will record the date and time of collection on the vial. Samples will be stored at room temperature by participants, until they can bring samples to the Prevention Center Clinic for their other assessments. At the Prevention Center, they will be placed in the -80°C freezer for long-term storage until assays are ready to be performed. [Participants who opt against a clinic visit will be provided with shipping materials, and the samples will be shipped overnight to the Prevention Center and placed in the -80°C freezer for long-term storage until assays are ready to be performed.](#)
- **Urinary norepinephrine:** Participants will collect urine over 24 hours. They will store the urine in provided bottles in their refrigerator (or cooler with ice pack) until they bring the collected urine to the Prevention Center for their clinic visit. At the Prevention Center, the sample volume will be recorded. EDTA (final concentration 1 mM) and sodium metabisulfite (final concentration 4 mM) will be added to the samples in order to prevent catecholamine degradation, and samples will be stored at -80°C. Additional aliquots of untreated urine and urine with boric acid (25mL of urine mixed with 250mg boric acid) will also be stored for possible future assays. 24-hour urine collection may be more valid to assess chronic stress than first-morning void. Participants will receive electronic reminders to collect their urine and saliva samples. [Participants who opt against a clinic visit will not perform the 24 hour urine collection due to logistical difficulties associated with shipping urine and processing which is best done immediately rather than delayed.](#)

Assays

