13.0 STATISTICAL CONSIDERATIONS

13.1 Study Design

Individuals with stage II-IV ovarian cancer (N=98) who have completed primary treatment within one to six months and are in clinical remission will be randomized to a 24-week home-based exercise program or wait-list control. The exercise prescription will consist of 150 minutes of moderate aerobic exercise (the equivalent of brisk walking or higher intensity) per week, with weekly telephone-based support by an exercise physiologist. The control group will continue their usual activities and will be offered the exercise intervention after 24 weeks. Baseline and 24-week assessments will include validated questionnaires assessing distress and health-related quality of life, serum levels of IL-6 and VEGF, salivary cortisol levels measured at bedtime for three consecutive days, and 24-hour urinary norepinephrine levels. Participants will also complete the questionnaires at 12 weeks to provide additional longitudinal data. Compliance to the intervention will be assessed by daily activity logs, actigraphs, and completion of weekly telephone calls.

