The parameter β_1 is of our main interest and represents the mean difference in the outcome change from baseline to follow-up between participants in the exercise group and participants in the control group, adjusting for covariates Z such as age and BMI. We will first assess β_1 without any adjustments for Z (unadjusted analysis), and then add Z (adjusted analysis). Under the null hypothesis of no difference between intervention and control on the changes in the outcome measure, β_1 is equal to zero. If the exercise intervention indeed results in a greater reduction/increase in the outcome measure of interest in the exercise group compared with the control group, then β_1 is different from zero. Our statistical inference on β_1 will use the standard large-sample approximation, namely, two-sided Z-test and Z-confidence intervals based on the limiting Gaussian distribution.

Our analysis will be based primarily on intention-to-treat principle, but with minor modifications for practical considerations. The principles of ITT analyses are (i) keep participants in the intervention groups to which they were randomized, regardless of the intervention they actually received; (ii) measure outcome data on all participants; and (iii) include all randomized participants in the analysis (107). However, if data of individuals are lost, or are unavailable for other reasons immediately after randomization, then we will not include these individuals in the analysis (modified intention-to-treat). Under the modified intention-to-treat principle, enrolled participants who were later found to be ineligible will not be included in the primary analysis. To take adherence into account, we will also perform per-protocol analysis which includes only individuals who are considered adherent to the intervention assignment. Per-protocol analysis will not be our primary analysis, and we will report in detail the criteria for exclusion of individuals.

If we encounter missing data due to drop out or assay issues, we will apply mixed model regression using the available data in the analysis. In general, our analysis based on available data will be similar to the analysis using the individuals who do not have missing data (complete-case analysis) if the missing data mechanism is completely at random (108). When the

Protocol 10045

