13.5 Additional Efficacy Hypotheses, Outcome Measures, and Statistical Methods

Our exploratory analyses will investigate the effect of the moderate exercise intervention on 24-hour urinary norepinephrine levels. We will use the above GEE model in this investigation to compare the mean changes from baseline to 24-weeks between the exercise intervention and control groups. We will assess the relationships between the change from baseline to 24 weeks in each of the distress or quality of life measures and change from baseline to 24 weeks in each of the biomarkers (IL-6, VEGF, salivary cortisol, urinary norepinephrine) based on the Pearson correlation. Also, we will investigate the association between changes in the outcomes from baseline to 24 weeks (distress, Quality of Life, biomarkers) and exercise adherence among participants in the intervention group. We will provide the mean change in the outcome by category of exercise adherence (\geq 150 min/week, 120-149 min/week, 90-119 min/week, 60-89 min/week, 30-59 min/week, and <30 min/week).

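### Urinary norepinephrine is not collected at remote visits, but section 13.5 analyses its change without reference to visit mode; the analysis set, the handling of week-24 gaps and the scope of the conclusion need stating.

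*Combined protocol and SAP*

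**What the plan says.** Section 8.1 lets participants choose the route: "participants will now be given a choice to have study assessments performed in clinic at the Prevention Center, or near to home/ at home". For those who avoid the clinic, the same section says "Urine collection, vitals, and anthropometrics will be omitted", and its norepinephrine paragraph repeats that "Participants who opt against a clinic visit will not perform the 24 hour urine collection". The footnote to the Study Calendar (Appendix C) agrees. Blood and saliva are still obtained remotely.

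On timing, 8.1 says "Baseline assessments will occur prior to randomization", while section 7.4 says participants in both arms "will complete end-of-study assessments either at clinic, or home-based".

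The design summaries in the synopsis, 3.3 and 13.1 carry no such exception. Section 13.1 lists, for baseline and week 24, "salivary cortisol levels measured at bedtime for three consecutive days, and 24-hour urinary norepinephrine levels".

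Section 3.3.2 makes change in norepinephrine from baseline to 24 weeks an exploratory endpoint. For its analysis, 13.5 says "We will use the above GEE model in this investigation to compare the mean changes from baseline to 24-weeks", and it also correlates norepinephrine change with changes in distress and quality of life. It names no analysis set. Section 13.2 introduces its missing-data methods with "If we encounter missing data due to drop out or assay issues, we will apply mixed model regression using the available data". It then lists regression or multiple imputation under missing at random and, for informative missingness, weighted estimation, last observation carried forward (LOCF) and pattern-mixture models.

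**The concern.** A change in norepinephrine can be observed only if both visits take place in clinic. The collection sections were adapted to remote visits, but the statistical section was not. A reader of 13.5 cannot tell which participants the comparison covers, or how urine omitted because of visit route is handled.

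The two visits raise different problems. A remote baseline is settled before randomisation, so it costs precision and narrows the population but does not unbalance the arms. A remote week-24 visit is settled afterwards, by participants who know their arm. Section 9.0 lets participants continue after recurrence, so health could also influence who travels. If the route is related to the unobserved norepinephrine change, and differently so by arm, the contrast is biased.

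At stake is an exploratory biomarker result, and the correlations built on it, being read as applying to all randomised participants when it describes those who attended clinic.

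**Working it through.** **Reproducing the plan's own figures.** The plan gives no sample size, SD or detectable difference for norepinephrine, so Table 1 in section 13.3 is used to confirm the method. Inputs: 39 per arm, 80% power, two-sided alpha 0.05/7. Formula: (2.690 + 0.842) × SD × sqrt(2(1-rho)) × sqrt(2/39). For the Perceived Stress Scale (SD 6.77, rho 0.5) this gives 3.532 × 6.77 × 1 × 0.2265 = 5.41, as printed.

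**Inputs for norepinephrine.** I start from 39 completers per arm. The rest are assumptions: two-sided alpha 0.05 (the endpoint is exploratory and outside the seven-test adjustment), 80% power, and rho 0.65, the middle of the plan's three values. The documents give no share q of completers without a urine pair, so 10%, 25% and 50% are shown, equal in both arms. Differences are in units of the SD of a single measurement, and m = 39(1-q) is the number of pairs per arm.

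**Formulas.**
- Change contrast, pairs only: 2.802 × sqrt(4(1-rho)/m).
- Change contrast from an available-data mixed model, if every participant without a pair has a baseline urine only: 2.802 × sqrt(2[(1-rho²)/m + (1-rho)²/39]).
- Week-24 value conditional on baseline: 2.802 × sqrt(2(1-rho²)/m).

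| q | m per arm | SE inflation 1/sqrt(1-q) | Change, pairs only | Change, available data | Conditional on baseline |
|---|---|---|---|---|---|
| 0 | 39 | 1.00 | 0.53 | 0.53 | 0.48 |
| 10% | 35.1 | 1.05 | 0.56 | 0.55 | 0.51 |
| 25% | 29.25 | 1.15 | 0.61 | 0.60 | 0.56 |
| 50% | 19.5 | 1.41 | 0.75 | 0.72 | 0.68 |

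The model in 13.2 leaves the baseline arm difference free, so with complete pairs beta_1 is the difference in mean change. Conditioning on baseline multiplies its variance by (1-rho²)/[2(1-rho)] = (1+rho)/2. This is 0.825 at rho 0.65, and 0.75 and 0.90 at rho 0.5 and 0.8.

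**Illustrative bias.** Suppose 20% of one arm and 40% of the other go remote at week 24, and their mean change differs by 0.5 SD of change from that of attenders. An attenders-only contrast is then off by 0.5 × (0.40 - 0.20) = 0.10 SD of change. With 39 × 0.80 = 31.2 and 39 × 0.60 = 23.4 per arm, the standard error is sqrt(1/31.2 + 1/23.4) = 0.27, so the shift is about 0.4 standard errors. All three inputs are assumed.

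**Fit of the 13.2 methods.** LOCF sets change to zero for someone with only a baseline urine, and has nothing to carry forward for someone with none. The wording on imputation leaves single imputation open, which overstates precision. Unweighted GEE generally needs data missing completely at random, which is hard to assume when participants choose the route. The modified intention-to-treat clause concerns data unavailable straight after randomisation, which does not describe a choice made at week 24.

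**The case against.** The strongest reply is that 13.2 already has what is needed: an available-data mixed model, multiple imputation, weighting, pattern-mixture models and a commitment to examine the missing-data mechanism. That stands in large part. A reader might infer that 13.2 has no remedy, or that it requires imputing values for people never asked for urine. The text supports neither. What is missing is a statement of which methods apply to urine omitted because of visit route.

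A reader might also infer that including participants with one urine sample contaminates beta_1 with between-person differences. It does not in itself: a mixed model that includes them is valid under missing at random and recovers some information, as the table shows. Bias requires informative missingness.

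Third, the design summaries may simply be incomplete. The exception appears in 8.1 and in the calendar, so staff face no operational ambiguity. That also stands, and the summaries need only be aligned.

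Fourth, the reasons given for remote visits are the pandemic and travel, neither tied to arm, and nothing in the documents shows differential choice. Nor do they say outright that the route is chosen separately at each visit. Section 7.4 and the introduction of the option during the trial make clinic-then-remote plausible; remote-then-clinic is conjecture. So the bias figure illustrates a mechanism and is not an estimate.

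**Conclusion.** The point holds in a limited form. Paired norepinephrine is confined to participants in clinic at both visits, 13.5 ignores this, and the week-24 part of the selection comes after randomisation. The loss of precision depends on an unknown remote share, and the 1/sqrt(1-q) figures apply to a pairs-only analysis. Bias is possible, but its direction and size cannot be derived from the documents.

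Two stronger readings should be resisted. The rule does not weaken the primary analysis: norepinephrine is exploratory and absent from Table 1, and blood and saliva are collected on either route. Nor does restricting the set to participants with a baseline urine by itself preserve the randomised comparison. It removes selection at baseline only. Participants without a week-24 urine still contribute nothing to a model of that value, so the result is unbiased only if week-24 urine is missing at random given baseline norepinephrine and arm.

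The definite gain is in precision: at rho 0.65 with 39 pairs per arm, conditioning on baseline lowers the detectable difference from 0.53 to 0.48 SD.

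**What to change.** In 13.5:
- Define the norepinephrine analysis set as randomised participants with a baseline 24-hour urine, and analyse the 24-week value conditional on baseline norepinephrine. State the missing-at-random assumption.
- Apply the pattern-mixture or weighted sensitivity analysis already in 13.2 to week-24 urine missing by visit mode. Do not rely on LOCF or single imputation for it.
- Report urine availability by arm and visit.
- Limit the norepinephrine conclusion and its correlations to clinic attenders.

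Align the synopsis, 3.3 and 13.1 with 8.1 by stating that urine is collected at clinic visits only. Settle these rules before results are seen.

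The cost is protocol and SAP wording, with no new data collection. Any participants with only a 24-week urine are left out, and the stated scope is narrower.

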9.0 SUBJECT DISCONTINUATION FROM STUDY

Subjects may be removed from this study at any time at their discretion. Subjects may also be removed from this protocol if they develop any untoward side effects from the study intervention.

Cancer recurrence does not mandate study discontinuation. If a subject develops cancer recurrence, they may still continue on the study if they are willing and able. Exercise is safe for individuals with cancer who are undergoing active treatments including chemotherapy. The exercise physiologist may alter their exercise prescription as needed based on the individual's functional ability and medical condition. If a participant desires to discontinue the study, she may discontinue the study at any time. If an individual desires to stop exercising but is willing to complete study assessments, she will complete originally planned study assessments (including clinic visit) at the originally specified time points.

An explanation for discontinuing the study is recorded for each subject discontinuing the study on the appropriate CRF/eCRF. Treatment in this study must be discontinued for any of the following reasons:

- if the PI decides to stop the study;
- at Investigator's discretion;
- at the subject's request;
- Grade 4 or life-threatening toxicity (See Section 11, Adverse Events) attributable to study intervention

Target enrollment is 98 participants, accounting for up to 20% drop-out. Power calculations are based on 78 participants. Additional subjects may be enrolled in the study to replace individuals who have dropped out in order to achieve the goal of 78 participants completing the study.

